**Table 5.1 Baseline characteristics: shell table**

	Overall	Control	SMS	
	n (%) or median (IQR)			
Clinic:				
Facility 1				
Facility 2				
Facility 3				
Facility 4				
Facility 5				
Facility 6				
Sociodemographic				
Age (years)				
<12 years of education				
Crowding ( $\geq 3$ people/room)				
Married / cohabiting				
Employed				
Shares phone				
Can read SMS unassisted				
Can write SMS unassisted				
Received SMS messages from other program				
Obstetric				
Primigravida				
Gestational age				
Mental health				
Elevated depressive symptoms				
Social support score				
Parenting confidence score				

### 5.3 Analysis of study endpoints

1. **Neonatal mortality.** Among live-born infants, the proportion who die in the first 28 days postpartum will be compared between arms by log-binomial regression. As a *secondary analysis* of this outcome, a Bayesian analysis will be conducted using Markov Chain Monte Carlo modeling to estimate the probability that the Mobile WACh NEO treatment effect exceeds a range of potential values. Models with a range of prior probabilities will be developed.
2. **Early neonatal mortality.** Among live-born infants, the proportion who die in the first 7 days postpartum will be compared between arms by log-binomial regression.
3. **Initiation of early breastfeeding.** Proportion of infants who initiate breastfeeding in the first hour of life will be compared between arms by log-binomial regression.
4. **Cessation of exclusive breastfeeding.** Time to first introduction of complementary foods will be compared between arms by Cox proportional hazards regression.
5. **Bath.** Proportion of infants who are bathed in the first 24 hours of life will be compared between arms by log-binomial regression.
6. **Application of substances to cord.** Proportion of infants who have any substance applied to their cord will be compared between arms by log-binomial regression.
7. **Maternal provision of Kangaroo Mother Care (KMC).** Among women whose babies were born at <37 weeks gestation or weighing <2500g, proportion of who provide KMC on  $\geq 10$  of the first 14 days that the baby is home will be compared by log-binomial regression.
8. **Maternal knowledge of neonatal danger signs.** The mean number of 8 neonatal danger signs correctly named by mothers at the 2-week and 6-week visits will be compared between arms by Poisson generalized estimating equations (GEE). Exploratory analyses will evaluate time-dependent effects by incorporating timepoint as an interaction term.
9. **Appropriate care seeking.** The proportion of illness episodes with danger signs where the infant attended the clinic and/or where the infant was hospitalized independent of neonatal danger signs in the first 18 weeks of life (study follow-up period). Illness episodes are based on maternal self-report and only include the most recent illness episode at the 6-week visit, or 2-week visit if data is unavailable at the 6-week visit. Differences in proportions will be compared between arms by log-binomial regression.
10. **Elevated depressive symptoms.** The proportion of mothers with score  $\geq 13$  on the Edinburgh Postnatal Depression Scale at the 2-week and 6-week visits will be compared between arms by log-binomial GEE. Exploratory analyses will evaluate time-dependent effects by incorporating timepoint as an interaction term.
11. **Social support score.** The transformed mean social support score (range 0-100) at the 2-week and 6-week visits will be compared between arms using linear GEE. Exploratory analyses will evaluate time-dependent effects by incorporating timepoint as an interaction term.
12. **Self-efficacy.** The summed parenting confidence score (0-45) at the 2-week and 6-week visit will be compared between arms using linear GEE. Exploratory analyses will evaluate time-dependent effects by incorporating timepoint as an interaction term.

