A tablet-based screening questionnaire will be used to assess eligibility and collect sociodemographic characteristics. Following enrolment in the RCT and randomization, a tablet-based enrolment questionnaire using an open-source tablet-based data collection system (Open Data Kit) will be used to collect enrolment data including: demographics, clinical and sexual history, family planning, experience with SMS and technology, social support, intimate partner violence, and depression.

At each visit, a standardized questionnaire will evaluate self-reported outcomes (Table 4), experience with the intervention (for intervention participants) and participant clinical characteristics that may be associated with the outcomes, such as delivery experience, maternal and child health status, breastfeeding, care-seeking, cord care, depression and social support. Between study visits, data will be abstracted from patient clinic records to ascertain clinical outcomes such as deliveries, clinic/hospital visits, and infant or maternal deaths (Table 4). The data will be abstracted from available facility records including MCH cards, facility registers (hospitalization, ANC, CWC, PNC), and EMR systems. The study nurses will review clinic records daily to check for deliveries and clinic visits from study participants. We have successfully employed this approach in a previous RCT, Mobile WACH-X (64). In addition to contributing to ascertainment of trial outcomes, abstraction of clinic records will enable personalization of messaging, for example initiating postpartum messaging after a participant delivers.

Medical extraction forms will be completed by data teams: delivery information, infant admissions, maternal health, infant health, maternal mortality, and infant mortality.

When the study team learns of an infant death through an SMS message, phone call or clinic record review, the study team will contact the participant to arrange a visit to conduct a verbal autopsy. Verbal autopsies will be performed about 6 weeks after the infant death, either in the clinic or at the participant's home based on their preference.

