#### a. Analyses based on survival analysis

Assuming alpha=0.05, 2-sided test, 1:1 allocation ratio, with a sample size of 2,500 per arm, and 10% attrition, we will have  $\geq 80\%$  power to detect a Hazard Ratio (HR) of 0.53 in neonatal mortality, assuming mortality of 23 per 1000 births in the control arm. Assuming alpha=0.0045 (Bonferroni-adjusted for 11 tests) and 2-sided test, we will have  $\geq 80\%$  power to detect a difference of 90.0% vs. 93.1% continued exclusive breastfeeding to 6 weeks.

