**Table 5.2 Summary of statistical analyses**

Outcome	Indicator	Timing	Statistical Analysis
Primary outcome			
Neonatal mortality	Death during 1 st 28 days of life	2 and 6 week visits, clinic record abstraction	Log-binomial regression
Secondary outcomes			
Early neonatal mortality	Death during 1 st 7 days of life	2 and 6 week visits, clinic record abstraction	Log-binomial regression
Initiation of early breastfeeding	Breastfeeding in 1 st hour of life	2 week visit	Log-binomial regression
Exclusive breastfeeding	Cessation of EBF in 1 st 6 weeks of life	2 and 6 week visits	Cox proportional hazards
Thermal care	Bath in 1 st 24 hours of life	2 week visit	Log-binomial regression
Cord care	No application of substances to cord	2 week visit	Log-binomial regression
Home provision of KMC	Any duration of skin-to-skin care on ≥10 of the first 14 days at home, among low birthweight or preterm infants	2 and 6 week visits	Log-binomial regression
Maternal knowledge of neonatal danger signs	Number of the 8 danger signs or symptoms successfully named	2 and 6 week visits	Poisson GEE
Appropriate care seeking	Proportion of illness episodes with danger signs where the infant attended the clinic and/or where the infant was hospitalized regardless of danger signs reported in study follow-up	2 and 6 week visits, ongoing record abstraction	Log-binomial regression
Depression	Score above diagnostic threshold (≥13) for Edinburgh Postnatal Depression Scale	Baseline, 2 and 6 week visits	Log-binomial GEE
Social support	Score using MOS Social Support Survey	Enrollment, 2 and 6 week visits	Linear GEE
Self-efficacy	Score using Self-efficacy in Infant Care Scale	Baseline, 2 and 6 week visits	Linear GEE

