# Compared by linear GEE

#### **5.4 MISSING DATA**

Based on the Mobile WACh NEO pilot, we expect 10% loss to follow-up between enrollment and the 6-week study visit. We anticipate that dyads who are lost to follow-up are more likely to be disengaged from care and have experienced adverse outcomes. We also anticipate missingness may differ by arm, with the intervention arm having higher retention. Sensitivity analyses will be conducted for the primary mortality outcome assuming all missing participants did or did not experience neonatal mortality. If missing data rates were unexpectedly appreciably higher than these rates, more nuanced sensitivity analyses would be considered, such as those that consider differing rates of neonatal mortality for the missing participants that differ by arm. Variables with >10% missingness will be multiply imputed by MICE.

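### The primary 28-day mortality proportion has no rule for infants last known alive before day 28; the implied complete-case handling favours the better-retained arm, by a small amount

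*SAP*

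**What the plan says.** SAP section 5.3, item 1, sets the primary analysis: "Among live-born infants, the proportion who die in the first 28 days postpartum will be compared between arms by log-binomial regression". Section 6 records that this replaced Cox regression on 8 October 2020, on the DSMB's recommendation. Protocol Table 4 still lists Cox.

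Status is ascertained at "2 and 6 week visits, clinic record abstraction" (SAP Table 5.2). No contact is scheduled at day 28. SAP section 2 names the sources that establish a death, but nothing says what establishes survival to day 28.

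On missing data, SAP section 5.4 says "we expect 10% loss to follow-up between enrollment and the 6-week study visit", and adds: "We also anticipate missingness may differ by arm, with the intervention arm having higher retention". The sensitivity analyses for mortality are run "assuming all missing participants did or did not experience neonatal mortality". MICE applies only to variables with more than 10% missing. The modification log justifies MICE by comparison with complete-case analysis, so complete case is the implied default at or below that threshold.

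The protocol (section 11.6) already abstracts records that could show an infant is alive, including "facility registers (hospitalization, ANC, CWC, PNC), and EMR systems".

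**The concern.** Deaths and survivals need different evidence. A death on day 5 is final after one contact or one record. Survival to day 28 needs evidence dated day 28 or later. Cox regression censors an infant last seen at day 14 and keeps its 14 days; a binary day-28 model must either drop that infant or assign it a value.

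Under complete-case handling, infants known to have survived the period of highest risk leave the denominator, while earlier deaths stay in the numerator. Each arm's risk is inflated in line with its loss after a live contact. If that loss is greater in the control arm, control risk is inflated more and the RR falls below its true value. The affected quantity is the primary estimate. The trial is also unblinded, so an unwritten rule for the primary denominator leaves a choice open after the data are seen.

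**Working it through.** **1. The plan's own figure.** SAP section 3a: "Assuming alpha=0.05, 2-sided test, 1:1 allocation ratio, with a sample size of 2,500 per arm, and 10% attrition", with at least 80% "power to detect a Hazard Ratio (HR) of 0.53 in neonatal mortality, assuming mortality of 23 per 1000 births in the control arm". Table 3.1 gives 12.2 per 1000 for the intervention arm. After attrition there are 2,250 per arm, so expected deaths = 2,250 × (0.023 + 0.0122) = 79.2. Schoenfeld's formula at HR 0.53 needs 78 events and gives 80.6% power. The figure reproduces, and 23 per 1000 is used below.

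**2. Inputs for the shift.**
- True risk r = 0.023 in both arms (null case).
- q = share of neonatal deaths before the 2-week contact, assumed 0.73 to 0.95. The lower end is the first-week share in Protocol Figure 3 (the SAP rationale gives 75%); the upper end is an assumption.
- L = share of 2-week survivors with no later status. The SAP gives a 10% average from enrolment, and neither an arm split nor timing. Assumed total loss is 13% control and 7% intervention (mean 10%). Either half falls after the 2-week contact (6.5%/3.5%) or all of it does (13%/7%).
- Loss after 2 weeks is taken as non-informative, to isolate this component.

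**3. Formula.** With d1 = qr and d2 = (1 − q)r:

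complete-case risk = [d1 + d2(1 − L)] / [d1 + (1 − d1)(1 − L)]

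Worked at q = 0.85, so d1 = 0.01955 and d2 = 0.00345:
- L = 0.13: 0.02255 / 0.87254 = 25.8 per 1000.
- L = 0.07: 0.02276 / 0.93137 = 24.4 per 1000. RR = 0.945.
- L = 0.065: 0.02278 / 0.93627 = 24.3 per 1000.
- L = 0.035: 0.02288 / 0.96568 = 23.7 per 1000. RR = 0.974.

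**4. Type I error.** Wald test on log RR, with SE = √[(1 − r0)/(n0·r0) + (1 − r1)/(n1·r1)] and n = 2,500(1 − L). The SE is about 0.185. At q = 0.85 the shift is 0.026/0.185 = 0.14 SE (half) or 0.056/0.186 = 0.30 SE (all).

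| Loss after 2 weeks (control/intervention) | RR, q = 0.73 | RR, q = 0.85 | RR, q = 0.95 | Two-sided type I error |
|---|---|---|---|---|
| 6.5%/3.5% | 0.977 | 0.974 | 0.971 | 5.2% to 5.3% |
| 13%/7% (upper value) | 0.952 | 0.945 | 0.940 | 5.8% to 6.3% |
| 10%/10% | 1.000 | 1.000 | 1.000 | no shift |

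A wider split of 15%/5%, all after 2 weeks, gives RR 0.90 to 0.92 and type I error 7.2% to 8.7%.

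**5. The planned bounds.** At 13%/7%, all after 2 weeks and q = 0.85, 2,500 live births per arm give 56.4 and 56.9 recorded deaths (control, intervention), and 318.6 and 171.6 infants with no day-28 status.
- All survived: RR = 56.9/56.4 = 1.009, so the shift is nearly gone.
- All died: RR = (56.9 + 171.6)/(56.4 + 318.6) = 0.61. Yet the later deaths expected among these infants are 2,500 × 0.00345 × L, or about 1.1 and 0.6.

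**6. A force in the other direction.** Suppose lost infants have twice the risk of retained ones and are never seen. Observed risk is then 0.023/(1 + L): 20.4 per 1000 at 13% and 21.5 per 1000 at 7%, so RR = 1.06.

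**The case against.** The SAP nowhere says that these infants are dropped. Its denominator is live-born infants, and section 4 calls for intention to treat on everyone randomised; read literally, both keep an infant seen alive at 2 weeks. That stands: exclusion is an inference from the MICE threshold and its justification. The literal reading still does not say what value such an infant receives.

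The SAP also has remedies: the all-survived analysis, MICE above 10% missing, and arm-specific assumptions if loss is well above expectation. Step 5 confirms that all-survived removes nearly all of the shift. It is a sensitivity analysis, however, and leaves the primary estimate unchanged. Expected loss equals the 10% threshold, so whether MICE would apply is open, and no imputation model using last-known-alive status is described.

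Loss of the relevant kind may be small. The 10% runs from enrolment in pregnancy, so it includes women lost before delivery and infants never seen. The protocol traces late visits by phone, and by home visit for the 6-week visit (home visits were suspended under the COVID-19 appendix). It allows visits by phone and reviews clinic records daily. The SAP accepts 6-week visits up to 18 weeks, so one late contact settles day-28 status. All of this stands, and it is why the 13%/7% row is an upper value.

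A reader might infer that the primary analysis is biased towards the intervention overall. The documents do not support that. SAP section 5.4 also expects lost dyads to have had more adverse outcomes, and step 6 shows that this can offset the shift.

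**Conclusion.** The point holds as a limitation of the primary method together with an unstated rule. It should be changed, but it does not by itself put the trial's conclusion in doubt. The binary day-28 model has no place for partial follow-up. Under the implied complete-case handling, arm-differential loss after a live contact favours the better-retained arm.

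The most defensible size is an RR of about 0.97 to 0.98 under the null (type I error about 5.2%), with 0.94 to 0.95 (about 6%) as the upper value for a 13%/7% loss. Equal loss gives no shift. These figures rest on an assumed arm split, an assumed share of loss after 2 weeks, 73% to 95% of deaths before 2 weeks, and non-informative loss. They describe one component; the sign of the total bias is not known.

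The all-died bound has a separate defect. As worded, it counts infants known alive at 2 weeks as deaths if they are classed as missing, so it is far wider than the available information requires.

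**What to change.** Keep the 28-day risk ratio and change how each arm's risk is estimated:
- Use Kaplan-Meier at day 28, censoring each infant at the last date known alive. Because SAP sections 4 and 5.2 call for covariate adjustment, use log-binomial regression with inverse-probability-of-censoring weights where covariates are kept.
- Count any dated evidence of life on or after day 28, from visits, phone contacts or abstracted records, as survival. Apply the rule identically in both arms.
- Limit the best- and worst-case analyses to infants and follow-up time that are truly unknown.
- Report by arm how many infants were last known alive before day 28, and when.

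The cost is SAP wording and a little programming. The visits and records are already collected, and the risk-ratio scale adopted on the DSMB's recommendation is kept. The drawback is that censoring must be assumed non-informative (given covariates, for the weighted version). The SAP itself doubts this, so the missing-data sensitivity analyses must stay.

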11.3 Study Population

Table 2. Summary of proposed eligibility, procedures and outcomes for study aims

Population	N	Inclusion Criteria	Data Collection
------------	---	--------------------	-----------------

RCT			
Pregnant women	5020	
 • Pregnant • 28-36 weeks gestation • Daily access to a mobile phone (own or shared) on the Safaricom network • Willing to receive SMS • Age ≥ 14 years • Able to read and respond to text messages in English, Kiswahili or Luo, or have someone in the household who can help • 	
 • Screening questionnaire • Enrolment and follow-up questionnaires • Content of SMS conversations with Mobile WACH system
Post-RCT IDIs			
Postpartum women	60	Intervention RCT participant	
 • IDI

Study populations for each of the aims are summarized in Table 2. Two study populations will be included in the study:

1. Pregnant women (Randomized controlled trial) (N=5020)

Inclusion criteria:

- Age ≥ 14
- Pregnant
- 28-36 weeks gestation
- Daily access to a mobile phone on the Safaricom network
- Able to read and respond to text messages in English, Kiswahili or Luo, or have someone in the household who can help

Exclusion criteria:

- Currently enrolled in another research study
- Previous participant in the Mobile WACH NEO RCT (i.e. with a new pregnancy)

To enhance generalizability, literacy will not be required if women have access to a partner or family member whom she would be comfortable to have read her the messages. This approach was developed in consultation with mothers in Kenya, who felt that involving their partner was acceptable and may engage more support, and has been successfully implemented in our previous Mobile WACH studies.

2. Postpartum women (post-RCT IDIs) (N=60)

A subset of intervention RCT participants will be invited to participate in IDIs after they complete the intervention to evaluate their experiences with the intervention.

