**Sites:** Bondo District Hospital (Siaya County), Rachuonyo District Hospital (Homa Bay County), Mathare North City Council Clinic (Nairobi County), Riruta Health Centre (Nairobi County).

**Sample Size:** 5,000 pregnant women will be randomized (2,500 per arm)

**Duration:** Follow-up through 6 weeks postpartum.

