## 2. STUDY ENDPOINTS

Primary study endpoints:

1. **Neonatal mortality** will be defined as death of a live-born infant within 28 days of birth, based on mother's report, verbal autopsy, or clinic records.

Secondary endpoints:

1. **Early neonatal mortality** will be defined as death of a live-born infant within 7 days of birth, based on mother's report, verbal autopsy, or clinic records.
2. **Initiation of early breastfeeding** will be defined as initiation of breastfeeding within the first hour of life, based on maternal self-report at 2-week postpartum study visit.
3. **Cessation of exclusive breastfeeding** in the first 6 weeks of life will be ascertained based on maternal self-report at the 2-week and 6-week visits.
4. **Bath** in the first 24 hours of life will be ascertained based on maternal self-report at the 2-week visit.
5. **Application of substances to cord** will be ascertained based on maternal self-report at the 2-week visit.
6. **Maternal provision of Kangaroo Mother Care (KMC)** will be defined as proportion of mothers with low birth-weight or preterm babies (<2500g or <37 weeks EGA at birth) who report the baby spent any time skin-to-skin with an adult on  $\geq 10$  of the first 14 days at home.
7. **Maternal knowledge of neonatal danger signs** will be defined as the number of the 8 neonatal danger signs correctly named at 2-week and 6-week visits.
8. **Appropriate care seeking** will be defined as the proportion of illness episodes with danger signs where the infant attended the clinic and/or where the infant was hospitalized independent of neonatal danger signs in the first 18 weeks of life (study follow-up period). Illness episodes are based on maternal self-report and only include the most recent illness episode reported at the 6-week visit or 2-week visit if 6-week data is unavailable.
9. **Elevated depressive symptoms** will be defined as a score  $\geq 13$  on the Edinburgh Postnatal Depression Scale (range 0-30) at 2-week and 6-week visits.
10. **Social support score** will be defined by MOS social support score (range 0-100) at 2-week and 6-week visits.
11. **Self-efficacy** will be defined by the Karitane Parenting Confidence Scale score (range 0-45) at 2-week and 6-week study visits.

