**Notes:**

1. *if any log-binomial regressions fail to converge, Poisson regression with robust standard errors will be used for all comparisons of proportions.*
2. *If data needs to be imputed, the exclusive breastfeeding analysis will be conducted using Poisson regression with time offset instead of Cox regression, as this is asymptotically equivalent and easier to implement.*

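### Women are randomised but mortality is analysed per live-born infant, with no rule for multiple births, so an unclustered model could give a slightly too small standard error

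*SAP*

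**What the plan says.** **Unit randomised.** SAP section 1 states that "5,000 pregnant women will be randomized (2,500 per arm"). Protocol 11.6 likewise allocates participants, that is, pregnant women.

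**Eligibility.** Protocol 11.3 lists two exclusions: current enrolment in another study, and "Previous participant in the Mobile WACH NEO RCT (i.e. with a new pregnancy"). Multiple pregnancy is not among them.

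**Unit analysed.** SAP section 2 defines the primary endpoint as "death of a live-born infant within 28 days of birth". SAP 5.3 item 1 uses the denominator "Among live-born infants, the proportion who die in the first 28 days postpartum", and item 2 uses "Among live-born infants, the proportion who die in the first 7 days postpartum". Each "will be compared between arms by log-binomial regression", and Table 5.3 reports both per 1000 live births.

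**Correlated data.** The SAP names GEE for outcomes measured more than once. Depressive symptoms, for example, "at the 2-week and 6-week visits will be compared between arms by log-binomial GEE". It names none for mortality. Under Note 1 to Table 5.2, if any log-binomial model fails to converge, "Poisson regression with robust standard errors will be used for all comparisons of proportions". The note does not say that those errors are clustered on the mother.

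**Twins.** Neither document mentions them. There is no index-infant rule, no definition of any death per mother and no cluster term.

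**The concern.** A mother with two live-born infants adds two records to the mortality model, always in the same arm. A log-binomial model with its usual standard error treats those records as independent. If the outcomes of a pair are positively correlated, the variance of the arm-level proportion is larger than the model reports. The confidence interval for the primary risk ratio would then be too narrow and the test somewhat too liberal. The error would run one way only, towards declaring a difference.

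The silence also leaves room for two analysts to follow the same SAP and report different primary intervals. One might keep both twins without clustering, another might cluster, and a third might take one infant per mother. The last choice would be troublesome if it were made after deaths were known.

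**Working it through.** **1. The plan's own figure.** SAP 3a and Table 3.1 give 2,500 per arm, 10% attrition, two-sided alpha 0.05, and 23.0 against 12.2 deaths per 1000, with power of at least 80%.

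- Expected deaths: 2,500 × 0.9 × (0.0230 + 0.0122) = 2,250 × 0.0352 = 79.2.
- Ratio: 12.2/23.0 = 0.5304, so |ln| = 0.634.
- Power = Φ(√(79.2/4) × 0.634 − 1.960) = Φ(0.861) = 80.5%. The stated figure reproduces.
- A two-proportion test with 2,250 per arm is closer to the planned log-binomial model and gives 78.7%.

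These calculations count one infant per woman and include no design effect.

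**2. Design effect.** Let t be the share of mothers with twins, m the ratio of twin to singleton risk, ρ the within-pair correlation and p the overall risk. The documents supply only p (0.023, the control rate); t, m and ρ are assumptions.

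- Singleton risk s = p(1 + t)/(1 − t + 2tm); twin risk w = m × s.
- Variance per mother of the sum of (outcome − p): V = (1 − t)[s(1 − s) + (s − p)²] + t[2w(1 − w)(1 + ρ) + 4(w − p)²].
- DE = V / [(1 + t)p(1 − p)]. The true SE is √DE times the naive SE.
- True two-sided alpha = 2[1 − Φ(1.960/√DE)].
- If m = 1, this reduces to DE = 1 + 2tρ/(1 + t).

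**3. Middle case: t = 0.015, m = 3, ρ = 0.3.**

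- s = 0.023 × 1.015/1.075 = 0.02172; w = 0.06515.
- Singleton part: 0.985 × (0.021245 + 0.000002) = 0.02093.
- Twin part: 0.015 × (2 × 0.060905 × 1.3 + 4 × 0.04215²) = 0.015 × 0.16546 = 0.00248.
- DE = 0.02341/(1.015 × 0.022471) = 0.02341/0.02281 = 1.026.
- SE ratio 1.013; alpha = 2[1 − Φ(1.935)] = 0.053.

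**4. Range.**

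| t | m | ρ | DE | True SE / naive SE | Two-sided alpha |
|---|---|---|---|---|---|
| 1% | 1 | 0.1 | 1.002 | 1.001 | 0.050 |
| 1.5% | 1 | 0.3 | 1.009 | 1.004 | 0.051 |
| 1.5% | 3 | 0.3 | 1.026 | 1.013 | 0.053 |
| 2% | 3 | 0.3 | 1.034 | 1.017 | 0.054 |
| 2% | 5 | 0.5 | 1.088 | 1.043 | 0.060 |
| 3% | 5 | 0.5 | 1.122 | 1.059 | 0.064 |

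In the last row the true SE is 5.9% larger than the naive one; put the other way, the naive SE is 1 − 1/1.059 = 5.6% too small. Perfect correlation at t = 3% and m = 5 lies outside the range taken here and gives DE 1.23 and alpha 0.077.

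The twin rate alone does not fix the answer. At t = 3% and ρ = 0.5, DE is 1.029 if twins carry ordinary risk and 1.122 if their risk is five-fold.

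**5. Check by simulation** (40,000 replicates per scenario, 2,250 mothers per arm). The unclustered test of the log risk ratio rejected a true null in 4.8% of replicates with no twins, 5.2% in the middle case and 6.3% in the last row of the table. A variance clustered on the mother gave 4.8-5.1% in every scenario.

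**6. Power with the honest variance.** In the middle case it moves from 80.5% to 79.5% (events formula) or from 78.7% to 77.6% (two proportions). In the last row of the table, two-proportion power is 73.9%.

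**The case against.** **Independence is inferred from silence.** A reader might take the SAP to say that twins are treated as independent. It does not say so. Other wording takes the woman or the pair as the unit: the Aim 1 hypothesis speaks of women having lower neonatal mortality, section 4 applies intention to treat to all participants, and the missing-data section refers to dyads and to missing participants. This stands as a caution, and the finding is a gap in specification. None of that wording selects an infant, however, and the live-born denominator and the rate per 1000 live births point the other way. Applied as written, the named model has no clustering.

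**The effect is small.** This also stands. With equal twin and singleton risk, 1.5% twin pregnancies and correlation 0.3, the true SE is only 0.4% larger and alpha is 5.1%. The 6.4% figure needs all three assumptions at the top of their ranges together.

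**Twins' share of deaths.** A reader might add, as a fact, that twins supply far more of the deaths than of the births. The documents give no figure for this. In the middle case it follows from the assumed three-fold risk (3.0% of infants and 8.4% of deaths), so it is an assumption and not evidence.

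**The robust fallback.** One might think that Note 1 already covers the problem. Robust errors computed infant by infant do not account for pairs unless they are clustered on the mother.

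**Conclusion.** The mismatch of units is in the text, and the stated mortality models make no allowance for it. The standard error would be too small if three things hold: both twins are counted, their outcomes are positively correlated, and the errors are not clustered. On the assumed ranges (1-3% twin pregnancies, risk ratio 1-5, correlation 0.1-0.5) the true SE is 0.1-6% above the naive one and the type I error is 5.0-6.4%, with about 1.3% and 5.3% in the middle case.

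It would be wrong to read this as showing that the type I error does exceed 5%, or that the primary analysis or the sample size is invalid. The documents do not establish the inputs, and in the middle case power changes by about one percentage point. The point is minor. It matters if the primary result is borderline, and it is worth correcting because it touches the primary interval and is easily closed.

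**What to change.** In SAP 5.3 items 1 and 2, state that all live-born infants are counted and that standard errors are clustered on the mother, or equivalently that GEE is used with an independence working correlation and the mother as cluster. Repeat this in Note 1 under Table 5.2, so that the robust Poisson fallback is clustered as well. Apply the same rule to any other endpoint to which both twins contribute a record, and report the number of multiple births by arm.

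A mother-level outcome or an index infant chosen by a rule fixed in advance would also close the gap. Either would change the denominator from the live births now specified.

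The change needs no new participants and no change to the sample size, provided the records already link each infant to its mother. For the main mortality models it is one option in the model statement. The wording takes slightly more care, because the fallback model, the Poisson model for imputed breastfeeding data and the Bayesian secondary analysis of mortality should each say how pairs are handled. Estimates stay the same under the independence working correlation; only the intervals and p-values move.
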